1 SYNOPSIS

Name of Investigational Study Product: BTRX-246040	
Title of Study: Phase 2a, Double-blind, Placebo-Controlled Study to Investigate the Safety, Tolerability, Pharmacokinetics, and Efficacy of BTRX-246040 in Parkinson's Disease Subjects with Motor Fluctuations	
Approximate Number of Planned Subjects: 24 subjects or 3 cohorts of 8 subjects each	Phase of Development: 2a
Length of Study: Treatment Duration is 1 day and total duration of the study is up to 36 days including the 28-day screening period	
Study Objective: The purpose of this study is to assess the safety, tolerability, pharmacokinetics and efficacy of BTRX-246040 in subjects with PD who have motor fluctuations and predictable early morning off periods. Safety Objectives 
• To evaluate the safety of single ascending doses of BTRX-246040 in PD subjects with motor fluctuations and predictable early morning off periods Tolerability Objectives 
• To assess the tolerability of BTRX-246040 in PD subjects with motor fluctuations and predictable early morning off periods  Efficacy Objectives: 
• To evaluate the effect of single ascending doses of BTRX-246040 on the clinical features of Parkinson's disease in levodopa-treated PD subjects with motor fluctuations and predictable early morning off periods	

Study Population:

Levodopa-responsive Parkinson's disease subjects with motor fluctuations and predictable morning OFF periods.

Study Design:

The study will consist of 3 sequential, single ascending dose cohorts of 8 subjects each with a 6:2 randomization to BTRX-246040 or placebo. The planned dosing for each cohort will be 40, 80, and 120 mg. After enrollment of the first cohort has been completed, doses for subsequent cohorts may be modified based on a review of the available data (safety, tolerability, efficacy, and PK) by an unblinded Dosing Review Committee (DRC). A similar review and determination of dosing for the subsequent cohort will be performed after completion of each cohort and based on all data available from previous cohorts.

Following signing of IRB-approved informed consent, screening, and acceptance by an Enrollment Authorization Committee, subjects in each cohort who meet entry criteria will present to the clinic on the morning of Day 1 in the practically defined OFF state (having withheld anti-parkinsonian medications after 10:00 PM the evening prior). Prior to dosing on Day 1, Subjects will be randomized to either placebo or BTRX-246040. Subjects will then be dosed with study drug and UPDRS Part III motor response, dyskinesia rating and ON/OFF status will be assessed pre-dose and every 30 minutes for 4 hours and then hourly for 4 additional hours (i.e., 8 hours total post-dose). Subjects who turn ON following study drug administration, and remain ON after 8 hours, should be called the next morning to record the time they turned OFF and took their first regularly scheduled anti-parkinsonian medications after study drug, to a maximum of 24 hours.

On Day 1 subjects will come to clinic in a fasted state and will be administered a standard low protein breakfast. [REDACTED]

Subjects who reach and remain in the ON state for 8 hours will resume their regularly scheduled anti-parkinsonian medications 8 hours post-dosing. Subjects should remain on study drug until they experience an OFF episode after a full ON for 8 hours. However, if after 4 hours post study drug dosing, a subject's motor symptoms are severe and not responsive to study drug, the subject's regularly scheduled levodopa dose and other anti-parkinsonian medications may be administered, if deemed necessary based on the judgment of the investigator. All subjects, whether they are administered their regularly scheduled anti-parkinsonian medication or not will continue with study procedures until the end of the observation period of 8 hours. Orthostatic vital signs will be assessed pre-dose and 2, 4, 6, and 8 hours after dosing.

Subjects will return to the clinic 7 days later (Day 8) for a follow-up safety visit.

Following completion of cohorts 1 and 2, a Dosing Review Committee (DRC) meeting will take place to review available unblinded safety, tolerability, efficacy and, if available, PK data and determine if it is safe to go up to the next higher dosage for the next cohort. At any point, the DRC can request that a dosage be repeated for safety or tolerability rather than increased.

Inclusion Criteria

1. Diagnosed with Parkinson's disease (consistent with the UK PD Society Brain Bank Criteria for the Diagnosis of PD)
2. Men or women ≥ 30 years old and ≤ 76 years old
3. Female subjects must be either surgically sterilized or 2 years post menopausal at screening
4. Modified Hoehn and Yahr scale ≤ 3 in the ON state
5. Montreal Cognitive Assessment (MoCA) Score ≥ 26
6. Currently has a clear and decisive response to levodopa, and receiving a stable dose of levodopa (at least 4 doses per day of levodopa or ≥ 3 doses per day of Rytary™ (Carbidopa and levodopa Extended-Release Capsules) for at least four weeks prior to screening)
7. Experiencing motor fluctuations during waking hours with at least 2 hours of OFF periods each day, including predictable early morning OFF periods, based on subject assessment
8. Able to participate in the study in the practically defined OFF state
9. All anti-parkinsonian medications maintained at a stable dose for at least 4 weeks prior to the initial Screening Visit with the exception of MAO-B inhibitors, which must be maintained at a stable level for at least 8 weeks prior to the screening visit
10. Approved by a central Enrollment Authorization Committee as meeting entry criteria and being a suitable candidate for the study
11. Male subjects agree to use a reliable method of birth control during the study and for at least 90 days following the last dose of BTRX-246040 or placebo.
12. Informed and given ample time and opportunity to think about his/her participation in this study and has given his/her written informed consent on an Institutional Review Board (IRB) or Independent Ethics Committee (IEC) approved consent form
13. Judged to be reliable and able to keep all appointments for clinic visits, tests, and procedures, including venipuncture, and examinations required by the protocol.

Exclusion Criteria

1. Diagnosis of secondary or an atypical Parkinsonian syndrome
2. Severe disabling dyskinesia
3. Clinically significant psychosis or hallucinations or history of psychosis in past 6 months
4. History of previous neurosurgery for PD
5. Currently or previously on Duopa/Duodopa
6. Currently taking apomorphine
7. Has a diagnosis or history of a substance related disorder per DSM-V criteria (including alcohol but excluding nicotine and caffeine), during the 12 months prior to the Screening Visit
8. Medical or recreational use of marijuana in the 6 months prior to the Screening Visit
9. Has tested positive at the Screening Visit for drugs of abuse (opiates, cannabinoids, methadone, cocaine, and amphetamines [including ecstasy])

10. Active suicidal ideation within one year prior to the Screening Visit as evidenced by answering "yes" to Questions 4 or 5 on the suicidal ideation portion of the Columbia-Suicide Severity Rating Scale (C-SSRS) or attempted suicide within the last 1 year
11. Current major depressive episode or a Beck Depression Inventory-II (BDI-II) score of > 19. Subjects receiving treatment for depression with antidepressants may be enrolled if they have been on a stable daily dose for at least 8 weeks before the Screening Visit and are clinically stable in the opinion of the PI
12. Currently or within 8 weeks of screening receiving bupropion
13. Exposure to neuroleptics (antipsychotic drugs) for more than 1 month within the past 2 years, or any exposure within the past year
14. Any malignancy in the 5 years prior to randomization (excluding successfully treated basal cell carcinoma of the skin or cervical carcinoma in situ)
15. Current or previous diagnosis of malignant melanoma or the presence of any suspicious skin lesion based on physical exam findings.
16. Any other clinically significant medical condition or circumstance prior to randomization that, in the opinion of the Investigator, could affect subject safety, preclude evaluation of response, interfere with the ability to comply with study procedures, or prohibit completion of the study (e.g., uncontrolled diabetes mellitus, renal or hepatic impairment, coronary artery disease, evidence of significant active cardiac, respiratory, or hematologic disease, cancer with < 5 year remission (excluding successfully treated basal cell carcinoma of the skin or cervical carcinoma in situ), chronic pain, fibromyalgia or gastric bypass).
17. Prior seizures (other than childhood febrile seizure) or other condition that would place the subject at increased risk of seizures or is taking anticonvulsants for seizure control.
18. History of serious head injury (e.g., skull fracture, cerebral contusion, or trauma resulting in prolonged unconsciousness), intracranial neoplasm or hemorrhage.
19. Orthostatic hypotension that is symptomatic or requires medication
20. Participation in another study of an IMP or medical device currently or in the last 30 days or within 5 half-lives of the IMP (whichever is longer) prior to Screening
21. Alanine aminotransferase (ALT) or aspartate aminotransferase (AST) levels $\geq 2x$ upper limit of normal (ULN) or glomerular filtration rate ≤ 60 mL/min at Visit 1 (screening)
22. Nephritic syndrome, end-stage renal disease (and using renal replacement therapy such as hemodialysis or peritoneal dialysis), or a serum creatinine ≥ 2 mg/dL (≥ 172 μ mol/L) at the Screening Visit
23. Any other clinically significant abnormalities (i.e., laboratory deviations requiring acute medical intervention or further medical evaluation) in laboratory results at screening including clinical chemistries, hematology, and urinalysis, that, in the judgment of the Investigator, should preclude a subject's participation at study entry.
24. ECG abnormalities at Visit 1 (screening) or Visit 2 that, in the judgment of the Investigator, are clinically significant related to the subject's participation
25. Using the following concomitant medications (contact the Sponsor-designated medical monitor to determine eligibility when in doubt):
 - a) proton pump inhibitors within 5 half-lives of Screening
 - b) fluoxetine and irreversible monoamine oxidase inhibitors within 4 weeks of Screening

- 26. Currently taking or have taken, within 5 half-lives of Screening, any medications or supplements that are strong inhibitors or inducers of CYP3A4.
- 27. A known hypersensitivity to gelatin capsules.
- 28. Investigator site personnel directly affiliated with this study, and/or their immediate families. Immediate family is defined as a spouse, parent, child, or sibling, whether biological or legally adopted.
- 29. Employees of the Sponsor or of any third-party organizations (TPOs) involved in study who require exclusion of their employees.
- 30. Have participated in a clinical trial or any other type of medical research judged by the Investigator to be scientifically or medically incompatible with this study within 30 days prior to Visit 1 (screening). Contact the Sponsor-designated medical monitor to determine eligibility when in doubt.
- 31. Previous completion or withdrawal from this study or any other study investigating BTRX-246040 (previously called LY2940094).

Investigational Study Product, Dose and Mode of Administration:

BTRX-246040 will be administered orally as follows:

- 40 mg (███████████) in Cohort 1
- 80 mg (███████████) in Cohort 2
- 120 mg (███████████) in Cohort 3

Reference Therapy, Dose and Mode of Administration:

Placebo will be administered orally at the same number of capsules as active drug at each Cohort. Placebo capsules will consist of inactive ingredients and look identical to BTRX-246040.

Planned Duration of Treatment:

Study drug will be administered once on Day 1

Criteria for Evaluation:

Safety: Will be assessed descriptively by adverse events reporting which will include AEs, SAEs, vital signs, laboratory values, physical and neurological exams, C-SSRS, and ECGs.

Tolerability: Will be assessed by percent who complete protocol

Pharmacokinetics: Descriptive review of Pharmacokinetic (PK) ██████████
███████████

Efficacy: Will be assessed descriptively for the following endpoints.

Primary Endpoint:

- Maximal change in UPDRS Part III from pre-dose to post-dose on Day 1

Secondary Endpoints:

- Duration of ON time on Day 1
- Percentage of subjects that turn ON on Day 1
- Time to ON on Day 1

- Area under the curve for UPDRS Part III during the 8 hours of assessment on Day 1
- Change from pre-dose dyskinesia rating (from the UPDRS Part III motor response and dyskinesia assessment)

Statistical Methods:

All data will be assessed descriptively as presented in the SAP, and no formal statistical comparisons will be performed.

Sample Size Calculation:

Formal sample size calculation will not occur. A sample size of 8 subjects per group is deemed sufficient to evaluate the preliminary safety, tolerability, and efficacy of the different dose levels.

TABLE OF CONTENTS

1	Synopsis.....	2
Table of Contents.....		8
2	Protocol Signature Page.....	14
3	Abbreviations.....	15
4	Introduction	18
5	Objectives.....	21
5.1	Primary Objective	21
6	Investigational Plan.....	22
6.1	Summary of Study Design	22
6.2	Study Design and Control.....	23
7	Study Population	24
7.1	Inclusion Criteria.....	24
7.2	Exclusion Criteria.....	25
7.2.1	Rationale for Exclusion of Certain Subjects	27
7.3	Discontinuations	27
7.3.1	Early Discontinuation.....	27
7.3.2	Discontinuation of the Study.....	28
8	Study Procedures.....	29
8.1	Visit 1: Screening.....	29
8.2	Visit 2: Treatment Period (Day 1).....	30
8.3	Visit 3: Safety Follow-up (Day 8 ±1)	31
8.4	Early Termination Visit	32
9	Treatment.....	33
9.1	Treatments Administered.....	33

9.2 Materials and Supplies.....	33
9.3 Method of Assignment to Treatment.....	33
9.4 Rationale for Selection of Doses in the Study.....	33
9.5 Selection and Timing of Doses.....	34
9.6 Blinding	35
9.7 Dosing Review Committee	35
9.8 Concomitant Therapies.....	35

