5 OBJECTIVES

5.1 PRIMARY OBJECTIVE

Safety Objective:

- To evaluate the safety of increasing doses of BTRX-246040 in levodopa-treated PD subjects with motor fluctuations and predictable early morning off periods

Tolerability Objective:

- To assess the tolerability of BTRX-246040 in PD subjects with motor fluctuations and predictable early morning off periods

[REDACTED]

[REDACTED]

[REDACTED]

[REDACTED]

Efficacy Objective:

- To evaluate the effect of increasing doses of BTRX-246040 on Parkinson's disease motor features of Parkinson's disease in levodopa-treated PD subjects with motor fluctuations and predictable early morning off periods

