6 INVESTIGATIONAL PLAN

6.1 SUMMARY OF STUDY DESIGN

The study will consist of 3 sequential, ascending dose cohorts of 8 subjects each with a 6:2 randomization to BTRX-246040 or placebo. The planned dosing for each cohort will be 40, 80, and 120 mg. After enrollment of the first cohort has been completed, doses for subsequent cohorts may be modified based on review of the available data (safety, tolerability, efficacy, and PK) by an unblinded Dosing Review Committee (DRC). A similar review and determination of dosing for the subsequent cohort will be performed after completion of cohorts 1 and 2 and based on all data available from previous cohorts.

Following screening and acceptance by an Enrollment Authorization Committee, subjects in each cohort who meet entry criteria and sign an IRB approved informed consent, will present to the clinic on the morning of Day 1 in the practically defined OFF state (having withheld anti-parkinsonian medications after 10:00 PM the evening prior). Prior to dosing on Day 1, subjects will be randomized to either placebo or BTRX-246040. Subjects will then be dosed with study drug and UPDRS Part III motor response, dyskinesia and ON/OFF status will be assessed pre-dose and every 30 minutes for 4 hours and then hourly for 4 additional hours (i.e., 8 hours total post-dose). Subjects who turn ON following study drug administration and remain ON after 8 hours, should be called the next morning to record the time they turned OFF and the time they took their first regularly scheduled anti-parkinsonian medications after study drug, to a maximum of 24 hours. Subjects who turn ON following study drug administration and subsequently turn OFF may be administered their regularly scheduled levodopa dose and other anti-parkinsonian medications.

Subjects who

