9.6 BLINDING

This is a double-blind study. Subjects, site personnel, and the Sponsor will be blinded to treatment.

The Investigator should make every effort to contact the medical monitor prior to unblinding a subject's treatment assignment. If an Investigator, site personnel performing the assessments, or subject is unblinded, the subject must be discontinued from the study. In cases where there are ethical reasons to have the subject remain in the study, the Investigator must obtain specific approval from the Sponsor-designated Medical Monitor for the subject to continue in the study.

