12 SAMPLE SIZE AND STATISTICAL METHODS

12.1 DETERMINATION OF SAMPLE SIZE

No formal sample size calculation is being calculated. A sample size of 8 subjects per cohort is deemed sufficient to evaluate the preliminary safety, tolerability, and efficacy of the different dose levels.

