12.2.8 SAFETY ANALYSES

Safety analysis will use the Safety Population. The overall safety and tolerability of BTRX-246040 treatment will be assessed by evaluating the safety and tolerability measures listed below.

For continuous variables, descriptive statistics (n, mean, SD, median, minimum, and maximum) will be provided for actual values and changes from baseline to each time point. For categorical

variables, subject counts and percentages will be provided. Summaries will be presented by treatment group.

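### The synopsis defines tolerability only as percent completing, which is a weak measure after one supervised dose and does not match section 12.2.8

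*Protocol*

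**What the plan says.** Tolerability is a separate objective in Protocol section 5.1, under the primary objective heading: "To assess the tolerability of BTRX-246040 in PD subjects with motor fluctuations and predictable early morning off periods". The synopsis (Criteria for Evaluation) gives its measure as "Will be assessed by percent who complete protocol". The same list places AEs, vital signs, laboratory values, examinations, C-SSRS and ECGs under safety.

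On treatment, the synopsis says "Study drug will be administered once on Day 1", and section 10.2.3 has study staff give the dose in the clinic. Sections 8.2 and 8.3 leave two things to complete after dosing: 8 hours of observation and one visit on Day 8 ±1.

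Section 12.2.8 takes a different route: "The overall safety and tolerability of BTRX-246040 treatment will be assessed by evaluating the safety and tolerability measures listed below". The items that follow are AEs, laboratory tests, vital signs, ECGs, physical examination, orthostatic blood pressure, C-SSRS and QUIP-RS. Percent completing is not among them. Section 12.2.8.1 tabulates TEAEs by system organ class and preferred term with both subject and event counts. Its breakdowns by severity and by relationship count events only, as percentages of all TEAEs.

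**The concern.** In a repeat-dose study, stopping treatment early carries information about tolerability. Here there is no second dose to refuse, reduce or stop, so completion loses most of that link. It can miss poor tolerability in subjects who stay to the end. It can also register poor tolerability where there was none.

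The protocol therefore gives one of its stated objectives a weak measure in one place and a different set of measures in another. A report that follows the synopsis could present a high completion percentage as the tolerability result. The AE tables that would qualify it do not, as specified, show how many subjects at each dose had a moderate, severe or related event.

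**Working it through.** **1. Planned numbers.** Section 6.1 gives "3 sequential, ascending dose cohorts of 8 subjects each with a 6:2 randomization to BTRX-246040 or placebo". That is 3 × (6 + 2) = 24, with 3 × 6 = 18 on active drug and 3 × 2 = 6 on placebo. It agrees with the synopsis total, "24 subjects or 3 cohorts of 8 subjects each". Section 12.1 says "No formal sample size calculation is being calculated", and no expected completion rate or tolerability threshold is stated, so there is no further figure to reproduce.

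**2. What the completion measure captures.**
- A subject with a severe AE who stays through Day 1 and attends Day 8 counts as a completer.
- A subject who goes back to usual anti-parkinsonian medication on Day 1 continues study procedures to 8 hours (section 8.2), so this does not by itself make a non-completer.
- Scheduled safety laboratory tests fall only at screening and Day 8 (Appendix 1). A discontinuation prompted by liver tests (section 7.3.1) would normally arise at the last visit, when it can hardly change completion.
- A subject may fail to complete through loss to follow-up, a sponsor decision or a physician decision (section 7.3.1), or through unblinding, where section 9.6 says "the subject must be discontinued from the study" unless the medical monitor approves continuation.

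**3. Resolution at 6 per dose.** Completion moves in steps of 1/6 = 16.7 points. If all n subjects complete, the exact two-sided 95% lower bound is 0.025^(1/n):
- n = 6 (one dose): 0.025^(1/6) = 54.1%
- n = 18 (all active): 0.025^(1/18) = 81.5%

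If 5 of 6 complete (83.3%), the exact 95% interval is 35.9% to 99.6%.

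**4. Insensitivity (assumed rates, not in the protocol).** Let q be the chance of a troublesome AE and s the share of those subjects who then fail to complete. Among 6 subjects:
- P(at least one troublesome AE) = 1 − (1 − q)^6
- P(at least one resulting non-completer) = 1 − (1 − qs)^6

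| q | P(≥1 AE) | P(≥1 non-completer), s = 5% | s = 10% | s = 25% | s = 100% |
|---|---|---|---|---|---|
| 20% | 73.8% | 5.9% | 11.4% | 26.5% | 73.8% |
| 33% | 91.0% | 9.5% | 18.2% | 40.3% | 91.0% |
| 50% | 98.4% | 14.1% | 26.5% | 55.1% | 98.4% |

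Completion is as sensitive as the AE count only if every affected subject drops out (s = 100%).

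**5. Lack of specificity (assumed rates).** Suppose 2% to 5% of subjects are lost for reasons unrelated to dose. All 6 at a dose complete with probability 0.98^6 = 88.6% to 0.95^6 = 73.5%. So with probability 11.4% to 26.5% at least one of the 6 is a non-completer although the dose was tolerated.

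**6. Event counts against subject counts.** Three severe events at one dose look the same in the severity table whether they came from one subject (1/6 = 16.7%) or from three (3/6 = 50%).

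**The case against.** The strongest reply is that section 12.2.8 already assesses tolerability jointly with safety, from AEs by severity and relationship, AEs leading to premature discontinuation, vital signs, orthostatic blood pressure and ECGs. A reader might infer from the synopsis alone that the tolerability objective cannot be answered. The protocol does not support that. The AE tables are introduced as a minimum, data are listed by treatment group and subject (section 12.2.1), and details are deferred to the SAP, which is not shown. This part of the reply stands. What remains is that the synopsis fixes a different and poorer measure, and that the tables the protocol does specify for severity and relationship give no subject counts.

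Three other stronger readings also fail.
- Completion does not show only who returned on Day 8. It also covers the Day 1 observation, and section 7.3.1 records reasons for discontinuation, with AE kept apart from loss to follow-up.
- Nothing says the Dosing Review Committee relies on the completion percentage. Sections 9.7 and 10.5.8 have it review the safety and tolerability data themselves, so severe AEs would be visible to it.
- A reading of 100% is not near certain. Even at an assumed 95% to 98% completion, all 24 subjects complete with probability only 0.95^24 = 29% to 0.98^24 = 62%.

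The study is also descriptive, so no test or decision rule depends on this line.

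**Conclusion.** The point holds as a weak stated measure and an internal mismatch. The synopsis ties tolerability solely to completion, and section 12.2.8 ties it to AE and safety measures without completion. After one supervised dose, completion is both insensitive and unspecific, and at 6 subjects per dose even a perfect result is compatible with a true completion rate as low as 54%.

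The mismatch, the event-only tables and the exact bounds follow from the protocol. The gap between 74% to 98% and 6% to 55% rests on assumed AE rates of 20% to 50% and assumed non-completion of 5% to 25% among those affected. It illustrates the direction and rough size and does not predict the result. The change is worth making because a stated objective is involved, but the defect does not invalidate the study or hide AEs from those reviewing them.

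**What to change.** Make the synopsis and section 12.2.8 agree. For each dose, beside placebo, assess tolerability as the number and percent of subjects with:
- a moderate or severe TEAE;
- a related TEAE, stating which of the five causality categories in section 10.2.2.2 count as related;
- early termination because of an AE.

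Keep percent completing as a disposition item under section 12.2.3. State whether placebo subjects are pooled over cohorts (6 subjects) or shown by cohort (2 each), since the protocol does not say.

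Severity, relationship and reasons for discontinuation are already collected, so no new data are needed and no dose or clinical rule changes. The cost is a small wording change in two sections and a few extra descriptive rows. The tolerability summary may also look less favourable than a completion percentage would.
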